9.0 STATISTICAL CONSIDERATIONS AND DATA MANAGEMENT

9.1 General Considerations

Data management and statistical analyses will be the responsibility of the Department of Biostatistics at IUSM. Parameter estimates and relevant summary statistics will be reported for both efficacy and side effects. Continuous variables will be summarized by means, medians, minima, maxima, and standard deviations. Categorical variables will be summarized by frequencies and percentages. Additional exploratory analyses will be performed when appropriate. Normality of variables will be checked and, if violated, nonparametric methods will be adopted. Changes from the analysis plan will not require an amendment to the protocol unless it changes a significant feature of the study. All analyses will be performed using SAS 9.4 (SAS Inc., Cary, NC).

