2.3.5 Depression treatment with *Beating the Blues* improves FMD and decreases inflammation

This recently completed pilot RCT, funded by a grant from the American Heart Association to [name], provides additional proof-of-concept and feasibility data. We hypothesized that treating depression with *Beating the Blues* before clinical CVD onset would improve endothelial function, as measured by FMD in [name] laboratory, and reduce inflammation in HIV-uninfected adults. Primary care patients (41-64 years, 52% female, 38% Black) with depression (PHQ-9 score ≥ 10) and no known clinical CVD were randomized to *Beating the Blues* ($n=13$) or usual care ($n=16$). We assessed FMD, circulating inflammatory markers, and depressive symptoms at baseline and 12 weeks. The 8 *Beating the Blues* sessions occurred between these visits.

	Beating the Blues Mean (SD)	Usual Care Mean (SD)	p	Cohen's d
Pre-treatment Level				
FMD, %	2.60 (4.18)	2.51 (3.00)	0.96	---
IL-6, pg/mL	4.15 (2.33)	4.90 (5.34)	0.73	---
SCL-20 (range: 0-4)	1.67 (0.78)	1.59 (0.96)	0.87	---
Post-Treatment Level Adjusted for Pre-Treatment Level				
FMD, %	4.18 (2.86)	2.47 (2.72)	0.21	0.61
IL-6, pg/mL	3.76 (1.65)	4.75 (2.84)	0.43	0.43
SCL-20 (range: 0-4)	0.83 (0.36)	1.44 (0.54)	0.02	1.33

As is shown in the Table, there were no meaningful differences between the groups in pre-treatment FMD, IL-6, or Symptom Checklist-20 (SCL-20) depression scores. As hypothesized, post-treatment FMD adjusted for pre-treatment FMD was higher in patients randomized to the intervention versus usual care ($p=0.21$, $d=0.61$). This difference was not statistically significant; however, the moderate effect size is clinically meaningful (123, 124). Similarly, post-treatment IL-6 levels adjusted for pre-treatment levels were lower in the

intervention versus usual care group ($p=0.43$, $d=0.43$ pg/mL). Although not statistically significant, this difference in IL-6 between groups are in line with levels associated with a greater risk of CVD events in the SMART trial (39% greater risk for each IL-6 increase of 0.34 pg/mL) (10). Finally, post-treatment SCL-20 score adjusted for pre-treatment score was significantly lower in the intervention versus usual care group ($p=0.02$, $d=1.33$), suggesting that *Beating the Blues* improved depression while improving FMD and lowering IL-6.

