9.3 Sample Size Justification

We calculated the trial's required sample size to achieve sufficient power to detect treatment group differences in FMD at Week 12. Using the effect size of *Beating the Blues* on FMD in our pilot trial, and assuming a power level of 0.80 with a Type I error of 0.05, we will need 88 participants (44 per arm) to detect an absolute difference in FMD of 1.7% at Week 12. This would be a clinically meaningful difference, as a 1.0% higher baseline FMD predicted a 6% lower risk of CVD events over five years in MESA (123, 124). We will increase the sample size to 110 (55 per group) to account for a conservative attrition rate of 20%. For the secondary outcomes of FMD (Week 24) and circulating IL-6, hsCRP, and D-dimer levels (Weeks 12 and 24), we will be able to detect effect sizes as small as 0.61 standard deviations.

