9.10 Analysis Plan for the Primary Objective

To test our primary hypothesis, an analysis of covariance (ANCOVA) will be performed to test for treatment group differences in Week 12 FMD adjusted for baseline FMD using the intent-to-treat set. Statistical significance will be considered if two-sided p-value <0.05. This analysis will be also repeated using the per-protocol set.

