9.11 Analysis Plan for Secondary Objectives

Both unadjusted comparisons and adjusted comparisons between UC and BtB will be performed for secondary outcomes defined in 1.2.1-1.2.3. For adjusted comparisons, multiple linear regression models will be constructed to include treatment group, baseline characteristics [demographics, SCL-20 scores, tobacco/exercise/adherence questionnaire results, ART drugs/regimens (including efavirenz (142-144)), antidepressant use, co-morbidities, CD4 cell counts, and HIV-1 RNA levels], and time-varying characteristics (changes in SCL-20 scores, questionnaire results, CD4 cell counts, ART drugs/regimens, HIV-1 RNA levels) to determine their effects on the outcomes. Pearson and Spearman correlation coefficients will be estimated for FMD, IL-6, hsCRP, D-dimer, circulating EPCs/ECFCs levels, and markers of monocyte activation (CD14+CD16+ cell proportions and sCD14/sCD163) with PHQ-9 and SCL-20 scores at baseline. These analyses will be performed for both the intent-to-treat set and the per-protocol set. Dose-response relationships between 12- and 24-week FMD and the number of BtB sessions, which have a range from 0 to 8, will be explored.

Safety assessments will be performed using the safety dataset. HIV-1 RNA levels and CD4 cell counts of the BtB arm during the trial will be summarized and compared to the UC arm.

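### The normality rule in section 9.1 leaves the replacement method unnamed and does not exempt the primary ANCOVA, so the baseline adjustment and the powered mean difference could be lost

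*Combined protocol and SAP*

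**What the plan says.** Section 9.1, which covers all analyses, states: "Normality of variables will be checked and, if violated, nonparametric methods will be adopted". It gives no test, no threshold, no list of variables and no replacement method, and it does not mention transformation. The same section adds: "Changes from the analysis plan will not require an amendment to the protocol unless it changes a significant feature of the study".

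For the primary objective, section 9.10 says that "an analysis of covariance (ANCOVA) will be performed to test for treatment group differences in Week 12 FMD adjusted for baseline FMD", with this criterion: "Statistical significance will be considered if two-sided p-value <0.05". It neither refers to the section 9.1 rule nor sets it aside.

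For the secondary outcomes, objective 1.2.2 compares 12- and 24-week changes in the biomarkers. Section 9.11 plans unadjusted comparisons and adjusted ones, in which "multiple linear regression models will be constructed to include treatment group" and a list of covariates. That list does not include the outcome's own baseline value.

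Section 9.3 sizes the trial on Week 12 FMD: "we will need 88 participants (44 per arm) to detect an absolute difference in FMD of 1.7% at Week 12".

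**The concern.** Three features of the rule matter.

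- **It looks at the wrong quantity.** The normality assumption of ANCOVA concerns the residuals, not the raw variables. A skewed outcome can have acceptable residuals, and at 44 per arm ANCOVA tolerates mild skew well.
- **The trial's own data choose the method, from an unwritten set.** Depending on that choice, the baseline covariate may or may not survive. A two-group rank-sum test has no covariate. A rank ANCOVA keeps one.
- **The quantity tested changes.** The sample size targets a mean difference of 1.7 FMD points. A rank-sum test addresses a shift in distribution, and no rank method directly estimates that difference. Nor does a simple rank test directly yield an estimate and standard error to pool after the multiple imputation planned in section 9.14.

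At stake are power in a design with little to spare, and a primary result on the scale that was planned. For skewed biomarkers, the unnamed fallback would in practice be the analysis.

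**Working it through.** **1. The plan's own figure.** Section 2.3.5 gives adjusted post-treatment FMD of 4.18 (SD 2.86, n = 13) and 2.47 (SD 2.72, n = 16). Pooled SD = √[(12 × 2.86² + 15 × 2.72²)/27] = 2.78, so d = 1.71/2.78 = 0.61. A two-sample t calculation with d = 0.61, two-sided 0.05 and 80% power needs 43.2, hence 44 per arm. Then 88/(1 − 0.20) = 110. Both stated figures reproduce. Power at 44 per arm is 80.8%.

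This d is baseline-adjusted: the pilot reports that "post-treatment FMD adjusted for pre-treatment FMD was higher in patients randomized to the intervention versus usual care". The 80% therefore relies on the adjustment being kept.

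**2. FMD if baseline is dropped, normal data.** Let r be the correlation of baseline with Week 12. The documents do not give it. If the unadjusted post-treatment SD equalled the pooled pilot baseline SD of 3.57, r = √[1 − (2.78/3.57)²] ≈ 0.63. The range used is 0.3 to 0.8.

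- Effect on Week 12 values: d√(1 − r²)
- Effect on change: d√(1 − r²)/√[2(1 − r)] = d√[(1 + r)/2]
- A rank-sum test multiplies either by √(3/π) = 0.977

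At r = 0.63, Week 12 values give 0.61 × 0.777 × 0.977 = 0.463, which has 57% power. Change gives 0.61 × 0.903 × 0.977 = 0.538, which has 70%.

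| r | Rank-sum, Week 12 | Rank-sum, change |
|---|---|---|
| 0.3 | 75% | 61% |
| 0.5 | 67% | 67% |
| 0.63 | 57% | 70% |
| 0.8 | 38% | 75% |

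Rank ANCOVA has about 75-79%. These powers apply once the switch has happened. Taking Shapiro-Wilk at 0.05 as the check (an assumption), normal data trigger it in only 4-6% of simulated trials, and power of the two-step procedure is 78-80%.

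**3. FMD with mild skew.** Assume gamma-distributed FMD with shape 6, d = 0.61 and r = 0.4-0.6. The check then fails in roughly 42-70% of simulated trials, depending on how the correlated skewed values are generated.

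| Analysis | Power |
|---|---|
| ANCOVA throughout | about 80-81% |
| Two-step rule, rank-sum fallback | 69-79% |
| Two-step rule, rank ANCOVA fallback | no loss (82-83%) |

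**4. IL-6.** Pilot pre-treatment values are 4.90 (SD 5.34, n = 16) in usual care and 4.15 (SD 2.33, n = 13) in the intervention arm. Under a lognormal shape, the log SD is √ln[1 + (5.34/4.90)²] = 0.885 and √ln[1 + (2.33/4.15)²] = 0.52. With either value Shapiro-Wilk rejects in over 99% of trials of 88 participants.

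The pilot d of 0.43 is also baseline-adjusted. Assume that it holds on the log scale, with r = 0.5-0.7. ANCOVA on logs then has 51% power in closed form. A rank-sum test of Week 12 levels has effect 0.43 × 0.866 × 0.977 = 0.364 at r = 0.5 (39% power) and 0.43 × 0.714 × 0.977 = 0.300 at r = 0.7 (29%). Simulation gives:

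| Analysis of IL-6, 44 per arm | Power |
|---|---|
| Log-scale ANCOVA | about 50% |
| Rank ANCOVA | 45-50% |
| Rank-sum, Week 12 levels | 27-41% |
| Rank-sum, change | 32-38% |

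**5. Type I error.** With no treatment effect and r = 0.63, every variant stayed at about 0.05 (0.044-0.058), for normal and for lognormal data.

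**The case against.** The strongest reply is that section 9.10 names ANCOVA for Week 12 FMD while section 9.1 is headed as general, so the specific section may be read as controlling. The documents also give no evidence that FMD is skewed: gamma shape 6 is an assumption, and with normal data little is lost. This stands as a limit on size. It does not remove the ambiguity, because neither section says which prevails.

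A reader might infer that the rule will discard the baseline adjustment. The text does not support that. It refers to nonparametric methods in general, and rank ANCOVA is one that keeps baseline and, for FMD, loses no power.

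A reader might also infer that biomarkers would lose a planned adjustment for their own baseline. None is stated: objective 1.2.2 concerns changes, and the section 9.11 covariate list omits the marker's baseline. Against an untransformed model the rule can even help. With log SD 0.885, r = 0.63 and d = 0.61, a rank-sum test of change had 69% power against 59% for raw-scale ANCOVA. The loss is clear only against log-scale or rank ANCOVA.

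The IL-6 skew is most marked in one pilot arm of 16. The other arm is less skewed, although its log SD of 0.52 still triggers the switch under the lognormal assumption. The documents give no distributional data for the other markers.

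**Conclusion.** The concern holds in a conditional form. The plan has a data-driven switch to an unnamed method, applied to variables rather than residuals and not excluded from the primary analysis. If the fallback is a rank-sum test, mildly skewed FMD would leave 69-79% power where ANCOVA keeps about 80-81%. If FMD is normal, or the fallback is rank ANCOVA, the power cost is small or nil, though a rank ANCOVA still does not estimate the 1.7-point difference. For IL-6 the switch is near certain under pilot-like skew, and the gap is about 50% against 27-41% between log-scale ANCOVA and rank-sum tests.

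Two stronger readings should be avoided. This is not a false-positive problem, since simulated type I error stayed near 0.05. Nor should the IL-6 effect of 0.43 be treated as unadjusted. Doing so would put log-scale ANCOVA at 63% (r = 0.5) to 80% (r = 0.7), but the pilot table reports the post-treatment levels as already adjusted for pre-treatment levels.

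The figures rest on assumed correlations, assumed gamma and lognormal shapes, Shapiro-Wilk at 0.05 as the check, and the pilot d for IL-6 carrying over to the log scale.

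**What to change.** State in sections 9.1 and 9.10 that the baseline-adjusted ANCOVA of Week 12 FMD remains the primary analysis whatever a normality check shows. Assess residuals with diagnostic plots, and name a robust, bootstrap or rank ANCOVA as a sensitivity analysis.

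For right-skewed biomarkers (IL-6, hsCRP, D-dimer and similar), pre-specify in section 9.11 an ANCOVA on the log scale with the log of the marker's own baseline as covariate, reported as a ratio of geometric means. Keep rank methods as sensitivity analyses.

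The cost is analysis-plan wording only, with no change to sample size or data collection. The downside is that biomarker effects are read as ratios, and any zero values need a stated offset.

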9.2 Study Design

This trial will be a randomized, controlled, single-blinded, two-arm, parallel group study. Eligible patients will be randomized 1:1 to either *Beating the Blues* (BtB) or Usual Care (UC). Stratifications for

randomization include usage of pharmacologic antidepressants at the Second Entry Visit and sex. Permuted-block randomization will be adopted to ensure the two arms are balanced. Randomization sequences will be prepared by the study statistician and forwarded to the study coordinator.

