3.2 Screening Visit

If deemed eligible for screening, the participant will be approached (with permission/referral of the potential participant's primary care provider) by either a study investigator or by an Infectious Diseases Research Clinic study coordinator to enter the screening phase of the study. After written, informed consent is provided by the participant, a random study code number will be assigned to the participant to ensure confidentiality. This study code number will be used for laboratory transport and processing, result reporting, and data recording.

The study participant need not be fasting for this visit. At the Screening Visit, the participant's medical, psychiatric, and medication history will be reviewed. A brief physical examination will be performed. The PHQ-9 questionnaire will be administered. If the potential participant is eligible based on these initial assessments, then blood will be drawn to determine if the participant meets the laboratory eligibility criteria (see Section 4.0). Urine pregnancy testing for female study volunteers of reproductive potential will also be performed. All screening tests will be performed at the Indiana Clinical Research Center (ICRC). If the eligibility criteria are met, then the participants will enter the clinical trial. For those who score ≥ 10 on the PHQ-9 and are thus eligible for study participation, we will notify their primary HIV provider of these results so that the provider may institute any additional management as deemed best. A list of local mental health service providers and clinics will be given to the patients' primary HIV providers or social workers.

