3.4 Second Entry Visit

This visit will occur within 30 days of the Screening Visit and will occur at the ICRC. During this visit, updated psychiatric management (such as new medical or behavioral therapies initiated since screening) and medications will be reviewed. The PHQ-9, SCL-20, International Physical Activity, Morisky, Tobacco Use, General Anxiety Disorder-7, Buss-Perry Aggression, PANAS (Positive Affect subscale of the Positive and Negative Affect Schedule), and Pittsburgh Sleep Quality Index questionnaires will be administered. **The study participant must be fasting for this visit.** Vital signs will be measured and a brief physical examination will be performed prior to performing the FMD procedure and obtaining blood for the circulating markers of interest. A urine pregnancy test will be repeated for women of reproductive potential. Urine will also be obtained for archiving.

Blood will also be drawn at this visit for archiving DNA for future studies of interest linking genetics with endothelial function and depression scores.

Randomization will occur at this visit. Randomization will be stratified by use of pharmacologic antidepressants at the time of the Second Entry Visit. The participants' primary providers will be notified of the randomization assignment.

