The procedure for measuring brachial reactivity will require at least one hour of the participant's time. There will be no documentation on the ultrasound scans indicating the randomization assignment of the study participants. This will ensure that [name], who will assess all the ultrasound results, will be blinded when reading the ultrasound scans. Female participants of reproductive potential will have their main study visits during the same phase of their menstrual cycle to minimize confounding by hormonal changes that may affect FMD results (128, 129).

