5.0 STUDY TREATMENT

5.1 Beating the Blues

To minimize treatment barriers, attrition, and subject burden, the BtB treatment sessions will occur in private at [name] laboratory, the ICRC, the Infectious Diseases Research Clinic at Eskenazi Health Hospital, or a remote location selected by the patient where s/he can access a computer with internet, such as the patient's home, the patient's work, a family member's/friend's home, or a public library. The location will be chosen by the participant. Patients will be provided with ear bud headphones if they plan to use them at remote locations and do not already own a pair of headphones that they would rather use. Up to 8 sessions will be performed between the Second Entry Visit and the Week 12 Visit. The PHQ-9 questionnaire will be administered at each of the Weekly BtB Sessions. No physiologic or biologic assessments will be performed during these sessions. The participants need not be fasting for these sessions.

At each in-person BtB session, a psychology research assistant trained in the use of this intervention will first collect homework and will start the appropriate session on a computer. The patient will then work through the session alone at his/her own pace. At the end of the session, the research assistant will give the patient the printed homework assignment and will schedule the next session.

Remote BtB sessions will be scheduled, just like in-person sessions. Patients who select the remote treatment option will be given a BtB binder with printouts of all future homeworks at the time of randomization (i.e., the end of the Second Entry Visit). To begin each remote BtB session, an assistant will call the patient to instruct the patient to put last week's homework in the BtB binder, to address any technical issues, and to ensure that the patient has launched the correct BtB session for that day. The patient will then work alone through the BtB session at his/her own pace, with the assistant monitoring progress remotely on the secure BtB website set

up for this trial. To end the session, the assistant will call the patient back to address any questions and ensure that the patient has identified the correct printed homework in the BtB binder.

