9.15 Data Management

A comprehensive web-based data management system will be developed for this study using REDCap by the IUCDCC which will allow controlled entry through the internet. REDCap provides a secure, web-based environment that provides an intuitive data entry interface and has real-time validation rules (with automated data type and range checks). The system offers easy data manipulation with logged auditing, functionality for reporting, monitoring and querying subject records. An experienced Database Administrator provides database creation, daily backup, and installation of security patches.

A unique identifier will be assigned to each study participant and their associated study specimens. Patient identifiers will be located only within the subject's study file in a separate, locked cabinet within the Infectious Diseases Research unit at the ICRC. Hardcopies of laboratory source records will also be stored in a locked file cabinet. All entryways to the IDRC are secured by padkey codes. Initial screening, consenting of potential subjects, and data abstraction and recording will be completed by either the primary investigators or by the research study coordinators from the IDRC.

The data management system will facilitate quality control efforts, prevent entry of erroneous values, provide warnings for possible outliers, generate missing data reports, track subjects and samples, and assist in the preparation of data for statistical analysis. All data will be reviewed and processed through multiple verification and edit checking programs post entry to ensure data quality.

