10.3 Adequacy of Protection Against Risks

10.3.1 Recruitment and Informed Consent

- Recruitment will only begin once the Indiana University Institutional Review Board has approved this study. All participants will be recruited from the outpatient HIV care clinics at Indiana University Health Hospitals and Eskenazi Health Hospital. Self-referrals from other venues will also be considered. If the primary caregiver for the patient believes he or she is eligible for the study and allows the patient to be

approached for screening, one of the study investigators or a study nurse will approach each potential participant during his or her regularly scheduled clinic visit. If eligibility is confirmed, then the purpose, procedures, and risks and benefits of the study will be discussed with the participant. Participants will have ample opportunity to ask questions and to have all concerns addressed. If the participant wishes to pursue screening, then written informed consent will be obtained (and a copy given to the participant). All consent forms will be stored in a locked file cabinet.

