Appendix: Suicide Management Plan

Suicide management plans very similar to the one described below have previously been approved by the Indiana University IRB and were successfully implemented in the two other depression trials conducted by our team (IRB #'s 1105005448 and 1110007119). Those suicide management plans were constructed with input from Eskenazi Midtown Community Mental Health Center leadership ([name], Associate Vice President, and [name]), who concluded that the plans provide a high level of protection while minimizing disruption to usual clinical activities. In the present trial, we will assess suicidal ideation at every study visit, and we are prepared to appropriately handle the situation should one of the enrolled patients exhibit suicidal ideation. Of note, zero enrolled participants in our two prior depression trials have exhibited suicidal ideation during their involvement in the studies, likely because patients exhibiting suicidality were not eligible to be enrolled, as is the case for the present trial.

(a) In-Person Study Visits

Suicidal ideation will be assessed using Item #9 of the PHQ-9 at the Screening Visit and all Main Study Visits (see Section 6.1). If a participant reports having thoughts of being better off dead or of hurting him/herself (i.e., responds with a 1, 2, or 3 to PHQ-9 Item #9 or spontaneously reports suicidal ideation) during the Screening, First Entry, Second Entry, Week 12, or Week 24 Visits, the visit will be immediately stopped, and the study coordinators ([name], [name]) running these visits will interview the participant to complete the Patient Suicidality Form (see below). If this interview is required at one of the Weekly BtB Sessions, the graduate student research assistants will perform this interview, as they will conduct these treatment sessions.

The study coordinators have been trained by [name], a clinical psychologist, in conducting the interview to complete the Patient Suicidality Form and in following this protocol. [name] will also serve as the primary supervisor to these study coordinators when it comes to their tasks related to this suicide management plan. In [name] completed (IRB #'s 1105005448 and 1110007119) and ongoing (IRB # 1411802537) clinical trials, he has trained ResNet research assistants to effectively conduct this interview and provide a high degree of protection to patients.

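### Section 9.2 sends the randomization sequences to the study coordinator, a role that shares in enrolment, and no section says how upcoming assignments are concealed

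*Combined protocol and SAP*

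**What the plan says.** - **Custody (9.2).** Randomization is 1:1 in permuted blocks, stratified by antidepressant use at the Second Entry Visit and by sex. No block size is given. On custody: "Randomization sequences will be prepared by the study statistician and forwarded to the study coordinator".
- **Approach (3.2).** Candidates are approached "by either a study investigator or by an Infectious Diseases Research Clinic study coordinator to enter the screening phase". Section 10.3.1 describes this step differently: "one of the study investigators or a study nurse will approach each potential participant during his or her regularly scheduled clinic visit".
- **Screening and consent (9.15).** "Initial screening, consenting of potential subjects, and data abstraction and recording will be completed by either the primary investigators or by the research study coordinators".
- **Visits (Appendix, Suicide Management Plan).** The list of study visits reads, in part, "Second Entry, Week 12, or Week 24 Visits, the visit will be immediately stopped, and the study coordinators ([name], [name]) running these visits".
- **Timing (3.4, Second Entry Visit).** "Randomization will occur at this visit". Section 5.1 places it at the end of that visit.
- **Masking (3.6).** "There will be no documentation on the ultrasound scans indicating the randomization assignment of the study participants". This keeps the scan reader unaware of the arm.

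**The concern.** Someone who enrols and knows the next assignment can let it influence whom to enter and when. Blocks and strata balance the arms in number and on the stratification factors; they do not stop that kind of selection. Here the only stated custody rule, followed literally, places the sequences with a role that takes part in enrolment, so this is more than a missing detail.

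The stake is comparability of the arms on traits that the analysis does not measure, such as motivation or expected adherence. The self-reported PHQ-9 and SCL-20 outcomes are plausibly more open to such selection than flow-mediated dilation (FMD). Analysis after enrolment cannot restore comparability on such traits.

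**Working it through.** The point is procedural and the plan states no figure to reproduce, so the check compares sections.

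**1. What is handed over.** Section 9.2 speaks of the sequences, not of individual assignments, and says nothing about the form in which they travel.

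**2. Who enrols.**

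| Step | Role named | Section |
|---|---|---|
| Receives the sequences | the study coordinator (singular) | 9.2 |
| Approaches candidates | investigator or coordinator | 3.2 |
| Approaches candidates | investigator or study nurse | 10.3.1 |
| Screens and consents | investigators or coordinators | 9.15 |
| Runs the Screening and both Entry Visits | study coordinators (plural) | Appendix |
| Randomization | at the end of the Second Entry Visit | 3.4, 5.1 |

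The nurse in 10.3.1 concerns the approach only; it does not take coordinators out of the other steps. Nothing separates the coordinator in 9.2 from those who enrol, and nothing shows that they are the same person.

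**3. Is concealment described anywhere?** The sections on randomization, enrolment, masking and data management mention no sealed envelopes, no central, telephone or web release, no independent holder of the list and no withholding of block sizes. Section 9.15 describes REDCap for data entry, validation, auditing and tracking, without an allocation function.

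**4. When would foreknowledge be usable?** The stratum depends on antidepressant use at the Second Entry Visit, which may fall up to 30 days after screening. The provider is told of the PHQ-9 result at screening and may start treatment meanwhile (3.2), and other entrants may use up list positions. Even an open list therefore does not reliably show, at approach or consent, what a candidate will receive. Close to the Second Entry Visit it can. What remains then is timing within the visit window, or not randomizing an eligible person. The judgment criterion 4.2.19 and the permission to re-approach or reschedule (end of 4.2) add a little room.

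**5. How much choice is there among candidates?** The Schema expects 3-4 entries a month, and 10.7 expects about 25% women. That gives 0.25 × 3 to 0.25 × 4 = 0.75-1 woman and 2.25-3 men a month, each group split again by antidepressant use. A second candidate in the same stratum will often not be at hand. The same slow accrual also means few intervening entries, so the protection in step 4 is partial.

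**6. What do existing safeguards cover?** Masked reading protects the measurement of FMD after allocation. ANCOVA on baseline FMD (9.10) removes only the part of a selected trait's effect that baseline FMD carries.

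**7. Why block sizes matter too.** Suppose blocks have a fixed, known size 2m (an assumption, since 9.2 gives no size). A person without the list who sees past assignments in a stratum can then deduce, on average, a share 1/(m+1) of the next ones: 50%, 33%, 25% and 20% for blocks of 2, 4, 6 and 8. These figures measure predictability, not bias.

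**The case against.** The strongest reply is that this is silence, not a shown defect. Forwarding the sequences is compatible with sealed or staged release, and a concealed procedure may sit in a working document. Section 9.2 names one coordinator while other sections have several, so the recipient may not enrol anyone. Approach needs the primary provider's permission or referral (3.2, 10.3.1), most eligibility criteria are objective, and the late fixing of the stratum blunts any list at the earlier steps.

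Most of this stands, and it limits the claim. It does not remove it. The plan names a recipient in an enrolling role and gives no condition on access, so a reader cannot establish from the document that allocation is concealed. If a sound procedure exists, stating it closes the point.

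**Conclusion.** The point holds as a cheap improvement. As written, 9.2 allows an enrolling role to hold upcoming assignments, and no section describes concealment. The exposure lies mainly close to the Second Entry Visit.

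A reader might go further and infer that allocation was open, that the person holding the list also enrolled, or that the FMD comparison is biased. The documents support none of these: they do not give the form of the list, do not identify its holder with an enroller, and contain nothing to show that any entry was steered.

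No bias figure is warranted. It would need the share of entries influenced and the relation of the selected trait to Week 12 FMD beyond baseline FMD, and the documents give neither. The recommendation rests on the low cost of the change.

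**What to change.** Replace the last sentence of 9.2 with:

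> The study statistician will prepare the randomization sequences, which will be kept by the statistician or by another named person not involved in enrolment. No one who approaches, screens, consents or enrols participants will have access to the sequences or block sizes. Each assignment will be released singly, by central or web-based release or by sequentially numbered opaque sealed envelopes prepared by that custodian, only after eligibility is confirmed and the Second Entry Visit baseline assessments (questionnaires, FMD images, blood) have been collected.

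The trigger is collection, not results, because FMD is read from stored images (3.6) and inflammatory and coagulation markers are tested in batches from frozen serum (6.1).

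This is Version 4.0, so sequences may already have been sent. If they went out in open form, new wording alone does not restore concealment: generate new concealed sequences for the remaining participants and report the change. If a concealed procedure is already in use, 9.2 should state its custodian, form and release step.

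Cost: a small one-time set-up and a custodian outside enrolment. Section 9.15 does not say that the REDCap build can allocate; if it cannot, envelopes or another central release are needed. Sample size, visits and analysis do not change.
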